3.6. Sample size

We will enroll 10 participants in the gabapentin trial. In personalized trials, sample size refers to the number of assessments for each patient. As we had no prior data from which to estimate within patient day-to-day variability in pain scores nor an expected effect size for symptom reduction when comparing gabapentin to placebo in this population, we did not calculate statistical power a priori for the number of assessments per treatment period. Rather, the sample size for each personalized trial was based on collecting the maximal amount of data expected to be tolerable from the perspective of patient study burden. Ten participants is a sampling number based on current recruitment into the PIUO Study (REB #H16-03288) from which we expect to draw the majority of participants for this trial. This number, with the repeated measures obtained throughout the treatment periods should provide sufficient data to address the study goals.

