Randomization will be undertaken by the study pharmacist, using a computer-generated randomization. Before the 2 periods (pair of active drug (G) or placebo (P)) the pharmacist will generate a random code indicating whether G or P is to be given first. The randomization table will be kept in the Research Pharmacy office, which has restricted access. In case of a serious adverse event and when necessary, the randomization of any one participant can be unmasked to the Principal Investigator. This will be done through direct contact between the pharmacist and the Principal Investigator.

Study Contacts

Contact with study participants during the trial will consist of online surveys and telephone check ins. Contacts will be scheduled to overlap with changes in dose. Each contact will last approximately 10 minutes. The following study tools will be used at study contacts (see table 4 for a schedule of assessments at the time of study contacts):

- Health Update (Appendix 6) (midway through each sequence and at study end)
- Pain Survey (Appendix) (only on the first or last day of each block, not both)
- NCCPC-R (Appendix 7)
- PROMIS-57 (Appendix 8)
- Adverse Events Log (Appendix 10)
- Concomitant Medications (Appendix 11)

When the participant begins Sequence 2, the drug will be dispensed again in person.

Follow up

Two weeks past Study End the randomization sequence for individual participants will be unblinded and shared with the participants along with their individual results. The results will be presented numerically and graphically. Graphs showing the outcomes over time on the medication and placebo arms, summarizing the dosage used at individual outcome points will be provided. This will allow participants to make decisions regarding continuing gabapentin (in consultation with their primary caregiver) and is in keeping the Strategies for Patient Oriented Research (SPOR) principles that this clinical care trial is based on. At this time, the participant's caregiver will also be given the opportunity to provide feedback to the research team via the Participation Questionnaire (Appendix 9).

For any participant that experiences a SAE, there will be an initial contact at the time of the event and appropriate evaluation undertaken by the physician investigator. Another safety follow-up visit will be scheduled within 7 days following the final study visit to review the event. Additional follow-up may be done based on the investigator's medical judgment.

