3.10. Statistical Methods

All data will be entered into a REDCap database, either directly from participants using a web-based entry system, or for those using paper, transferred from data collection sheets by a research assistant. The study cohort will be described in tables with descriptive statistics (mean, median and standard deviation) where appropriate. The primary method of analyzing the data was by systematic visual graphing of the pain scale over the exposure/placebo conditions. This is the method recommended by the CONSORT collaboration, extension for N-of-1 studies (CENT).⁵⁸

Data analysis for the primary outcome will be conducted within each N-of-1 trial and will also be aggregated across trials using measurements taken on days 11-19.

For each individual, the pain and irritability score on the NCCPC-R will be calculated over days 11-19 for both the treatment and control periods. These means will then be compared statistically using a Bayesian model, reporting the posterior mean difference using a non-informative prior for the means and variance. The posterior probability that the mean of the treatment is greater than the mean of the control will also be reported. Because of the use of non-informative priors, this analysis is very similar to a t-test.

We will also aggregate the means across participants using Bayesian linear mixed models in order to compare the average effect of the treatment as well as obtain better estimates of each individual's effect through borrowing of strength from others' data.

Additional analyses

Secondary outcomes will be assessed as follows:

- For each patient who benefits from gabapentin, the lowest dose that was effective in reducing pain scores will be calculated as the lowest dose that gives at least an 11 point reduction with no rebound over 3 days in the NCCPC-R score compared to baseline during day 11-19 on active drug. The set of lowest doses will be summarized descriptively.
- For each patient who benefits from gabapentin, the maximal effect dose will be calculated as the dose that gives the largest improvement in the NCPCC-R score compared to baseline during days 11-19 on active drug. The set of lowest doses will be summarized descriptively.

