- The latency time in days to the onset of maximum relief of pain and irritability as measured by the NCCPC-R score will be the day that gives the largest improvement in the NCPCC-R score compared to baseline during days 0-19 on active drug. The set of latency times will be summarized descriptively.
- Adverse Events will be compared between treatment arms descriptively.
- PROMIS-57 scores reported by parent/caregiver will be computed for each patient on each arm by averaging the scores taken on days 12, 16 and 19 and comparing these mean scores. The differences in mean scores between the treatment and placebo arms will be summarized descriptively.

Analysis population and missing data

For the primary outcome, any missing days will be excluded from calculation of the mean.

For secondary outcomes, missing values will be disregarded in the sense that only observed values will be used to compute the lowest dose, maximal effect dose, latency time and PROMIS-57 mean scores.

Analyses will use the intent-to-treat principle meaning that observations in a period will be ascribed to the treatment to which that period was randomized.

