^{*}If the child participated in the PIUO Study within the last 6 months these items will already be completed and only a Health Update is necessary to complete prior to drug dispensing. If the child did not participate in the PIUO Study all items will be completed and the PIUO Pathway will be implemented prior to drug dispensing. If a treatable cause for the child's PIUO is uncovered, the child will be withdrawn from the gabapentin trial.

Version 3.0 October 4, 2020 Page 39 of 45

 Table 4: Medication and Placebo Assessment Schedule for all subjects

Day	Health Update	Concomitant Medications	NCCPC-R	Pain Survey	PROMIS-57
1	X	X	X	X	X
2					
3					
4					
5			X	X	
6					
7					
8			X		
9					
10					
11	X		X		
12			X	X	X
13			X		
14			X		
15			X		
16			X	X	X
17			X		
18			X		

Version 3.0 October 4, 2020 Page 40 of 45

19			X	X	X
20					
21					
22			X		
23					
24					
25					
Switch Over*	X	X	X	X	X

^{*}Day 1 or 26 if switching over, not both

Version 3.0 October 4, 2020 Page 41 of 45

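### The per-child analysis in section 3.10 treats up to nine consecutive daily scores as independent, so each child's posterior is too narrow if the days are positively correlated

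*Protocol*

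**What the plan says.** Section 3.10 makes visual graphing the primary method and adds a model for each child. The day 11-19 means on the two treatments are compared "using a non-informative prior for the means and variance", and the posterior mean difference is reported. A second quantity follows: "The posterior probability that the mean of the treatment is greater than the mean of the control will also be reported". The section then describes the model: "Because of the use of non-informative priors, this analysis is very similar to a t-test".

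Table 4 in section 6.2, headed "Medication and Placebo Assessment Schedule for all subjects", marks the NCCPC-R on each day from 11 to 19. On incomplete data, section 3.10 says that "any missing days will be excluded from calculation of the mean". Under section 2.3 each child has one gabapentin and one placebo period.

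Across children, section 3.10 says: "We will also aggregate the means across participants using Bayesian linear mixed models". In section 3.6 the authors write that "we had no prior data from which to estimate within patient day-to-day variability in pain scores". Section 3.8 (Follow up) unblinds each child's sequence after Study End and shares the individual results with the family, to help them decide about continuing gabapentin: "The results will be presented numerically and graphically".

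**The concern.** Because each child has a single period per treatment, the days within a period are the only replication behind that child's posterior. A normal model with two means and one variance takes its standard error from the day-to-day scatter and treats each day as a fresh observation. Scores given by the same parent on consecutive days may well resemble one another. If they do, nine days carry less information than nine independent observations, and the posterior difference and probability look more certain than they should.

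The result for the individual child is a stated purpose of the N-of-1 design in section 6.2, and individual results go to families. Overstated certainty about one child is therefore the relevant harm.

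**Working it through.** **Inputs**

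- Scores per period: n = 9 at most (Table 4; missing days drop out).
- Periods per child: one per treatment (section 2.3).
- Model: two means, a variance (taken as common) and non-informative priors (section 3.10).
- Day-to-day correlation: not in the protocol. Assumed AR(1) with lag-1 correlation ρ, shown over a range. The daily SD cancels.
- The protocol states no power, interval width or posterior threshold for this analysis, so it has no figure to reproduce.

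**Step 1: the model as written.** With flat priors on the means and the usual reference prior on the variance, the posterior of the difference is a t distribution with 2 × 9 − 2 = 16 degrees of freedom. It is centred on the observed difference with scale s√(2/9). This is numerically the two-sample t-test, as the protocol says. Simulated with independent days, the 95% interval covers 95.0%.

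**Step 2: information in nine correlated days.** The variance of a nine-day mean is inflated by D = 1 + 2 Σ(k=1..8) (1 − k/9) ρ^k. At ρ = 0.5, D = 2.56, so nine days are worth 9/2.56 = 3.5 independent days.

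**Step 3: true against reported SD.** Positive correlation also shrinks the within-period variance: E(s²) = σ²(9 − D)/8. At ρ = 0.5 this is 6.44/8 = 0.805σ². The ratio of true to reported SD is √(D / [(9 − D)/8]) = √(2.56/0.805) = 1.78.

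**Step 4: a reported probability of 0.95.** The 0.95 point of t on 16 df is 1.746. At ρ = 0.5, 1.746/1.78 = 0.98, which corresponds to a probability of about 0.83.

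**Step 5: coverage and false signals.** These come from 200,000 simulated children with no effect at each ρ. The last column uses a cut-off of 0.95 in one direction, for illustration only; the protocol sets none.

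| ρ | D | Effective days | True/reported SD | Coverage of nominal 95% | 0.95 is worth | No-effect child exceeds 0.95 |
|---|---|---|---|---|---|---|
| 0 | 1.00 | 9.0 | 1.00 | 95% | 0.95 | 5.0% |
| 0.2 | 1.43 | 6.3 | 1.23 | 90% | 0.91 | 8.8% |
| 0.3 | 1.72 | 5.2 | 1.38 | 86% | 0.89 | 11.2% |
| 0.5 | 2.56 | 3.5 | 1.78 | 74% | 0.83 | 17.3% |
| 0.7 | 4.01 | 2.2 | 2.53 | 57% | 0.75 | 25.4% |

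**Sensitivity.** At ρ = 0.5, coverage is 75.3% with six scored days per period and 75.9% if days are paired across periods, so neither change matters much. At ρ = −0.2 the error reverses: D = 0.70 and coverage is about 98%.

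**The case against.** **The text may fix less than this.** The protocol never states that days are independent, and the t-test sentence is offered as a remark about priors. Residual covariance is often left to a statistical analysis plan, which is not shown here. This stands in part. But the protocol names the parameters and likens the result to a t-test, so a plan that added a correlation would depart from that sentence.

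**The consequence is limited.** The estimated difference is unbiased, visual graphing is primary, and no threshold or decision rule depends on the posterior. All of this stands. It limits the importance of the error but does not correct a posterior that section 3.10 still requires for every child.

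**Stronger readings that the documents do not support**

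- A reader might infer that families will be given overstated probabilities. Section 3.8 promises numerical and graphical results and does not say that the posterior probability is among them.
- A reader might infer that the mixed model carries the same error. That depends on its input. Section 3.10 speaks of aggregating means but also of aggregating across trials with the day 11-19 measurements. With one mean per child per period, the group mean effect is little affected. The individual estimates that borrow strength are exposed only if they use daily scores, or a variance from them, under independence.
- A reader might infer that the scores are in fact strongly correlated. The protocol has no data on this.

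**A shared correlation sits awkwardly with the design.** The trial is justified by differences between children, and results are released child by child. Both points stand and shape the fix.

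**Conclusion.** The point holds in conditional form. Followed as written, section 3.10 gives each child a posterior that is correct only if days within a period are independent, and the protocol offers no basis for assuming that. Under positive AR(1) correlation the posterior SD is too small by a factor of about 1.2 at 0.2, 1.4 at 0.3, 1.8 at 0.5 and 2.5 at 0.7. At zero correlation there is no error.

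The point concerns the width of each child's posterior and the posterior probability. It does not concern the estimated difference, the graphs or, on the reading of one mean per child per period, the group effect. That a single gabapentin-placebo pair cannot separate drug from period is a different matter, which modelling the correlation does not cure.

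The text should be changed, because the correction is specific and cheap. Confidence in the practical size is only moderate, since the correlation is unknown.

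**What to change.** **Final analysis (section 3.10).** Fit the per-child comparison to the daily day 11-19 scores with a serial residual correlation, for example AR(1), shared across children. Keep the planned means, variance and non-informative priors, and delete the t-test sentence. State whether the mixed model takes period means or daily scores. If it uses daily scores or their variance, give it the same residual correlation.

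**Family reports (section 3.8).** Table 3 places Study End at day 26 of the child's own second period, so results are released before a correlation shared by ten children can be estimated. Either give families the graphs and mean difference only, or label any early posterior probability as provisional and as assuming independent days. Report the correlation-adjusted posterior when all children have finished.

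**Cost.** A little more modelling; no added children or data. In simulations with ten children:

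- The adjusted interval covers 95% to 96% for correlations from 0 to 0.7.
- The median per-child posterior SD grows about 2% if days are independent, and about 1.4 and 1.9 times at correlation 0.3 and 0.5. That growth is the uncertainty now left out.
- If the model were fitted with only one or two children available, the SD would grow about 1.5 and 1.15 times even at zero correlation. This is why it belongs in the final analysis.

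**Limits to state.**

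- The active schedule changes dose inside days 11-19. A response to those steps would be read partly as correlation and make intervals too wide: coverage of about 97% with a one-SD step on days 18-19, and above 99% with a trend of 0.3 SD per day.
- If the correlation differs between children, coverage falls slightly, to 93% to 94% in the cases checked.

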2.2. Objectives

The primary objective of the trial is to evaluate the effectiveness of gabapentin to decrease pain and irritability in children with SNI, when the source of pain and irritability is attributed to neurological dysregulation (nociplastic pain), as measured by parent reported pain scores. This objective corresponds to the primary outcome listed in section 3.4.1.

We will compare the gabapentin versus placebo along an escalating dose range for both individual subjects and for the group. We will aggregate the results of the completed N-of-1 trials across all subjects to estimate the group level comparative effectiveness of gabapentin in reducing pain and irritability.

The secondary objectives are to:

- 1. Identify the optimal dosing of gabapentin in reducing pain and irritability (Corresponds to secondary outcomes 3.4.2 and 3.4.3).
- 2. Identify the latency time for gabapentin to show effectiveness (Corresponds to secondary outcome 3.4.4).
- 3. Evaluate the safety and tolerability of gabapentin (Corresponds to secondary outcome 3.4.5).
- 4. An Exploratory objective will be to evaluate whether parent/caregiver stress and function improve if gabapentin reduces children's pain and irritability. This objective corresponds to the Exploratory outcome listed in section 3.4.6.

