The risk of serious side effects of respiratory depression with concomitant use with opioids is acknowledged (BC Children's Hospital Integrated Pain Service Gabapentin Information http://www.bcchildrens.ca/Pain-Services-Site/Docu-Sheet. Accessed at: ments/BCCH1455Gabapentin.pdf. Retrieved on October 4, 2020). A minority of patients might be on opioids. Dose adjustments will be added when gabapentin is used with a concomitant opioid or other CNS depressant medication: the family will be advised to return to the previous stable, safe dose in the protocol, and the subject will remain at that dose with no further escalation for the duration of the trial arm. This schedule will be duplicated on the parallel arm (active drug or placebo) to maintain masking. The participants are highly monitored, often with continuous oxygen saturation monitoring and/or "baby-cam" devices observing them during sleep. During the daytime they are with family, or professional caregivers (aides, nurses, etc.). These individuals will be advised to watch for respiratory depression and sedation that occur well before fatal apnea, and how to respond.

While there are no prohibitions on concomitant care, any care or medications unrelated to the trial will be noted in the CRFs for each participant.

Participants are sometimes obtaining respite care at facilities with nursing and physician care. Medical reconciliation is done at each admission. Parents will be provided with a letter to share with these programs outlining the study, the drug being tested, and a 24-hour pager to contact for further information or concerns

Active Participants < 15kg in mg per kg

Day	Morning mg/kg	Noon mg/kg	Evening mg/kg	Total mg/kg per day	% Change
1*	0	0	5	5	0
2	0	5	5	10	100%
3	5	5	5	15	50%
4	5	5	5	15	0%
5	5	5	10	20	33%
6	5	5	10	20	0%
7	5	5	10	20	0%
8	10	10	10	30	50%
9	10	10	10	30	0%
10	10	10	10	30	0%
11	13.3	13.3	13.3	40	33%
12	13.3	13.3	13.3	40	0%
13	13.3	13.3	13.3	40	0%
14	17	17	17	50	25%
15	17	17	17	50	0%
16	17	17	17	50	0%
17	20	20	20	60	20%
18	20	20	20	60	0%
19	20	20	20	60	0%
20	13.3	13.3	13.3	40	-33%
21	6.7	6.7	6.7	20	-50%
22	0	5	5	10	-50%
23	0	0	5	5	-50%
24	0	0	0	0	-100%
25	0	0	0	0	0%
Switch over*	-	-	-	-	-

^{*}Day one or 26 if switching over, not both.

Active Participants > = 15kg in mg per day

Day	Morning mg	Noon mg	Evening mg	Total mg/kg per day	Total mg/day	% Change
1*	0	0	75	5	75	0
2	0	75	75	10	150	100%
3	75	75	75	15	225	50%
4	75	75	75	15	225	0%
5	100	100	100	20	300	33%

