6	100	100	100	20	300	0%
7	100	100	100	20	300	0%
8	150	150	150	30	450	50%
9	150	150	150	30	450	0%
10	150	150	150	30	450	0%
11	200	200	200	40	600	33%
12	200	200	200	40	600	0%
13	200	200	200	40	600	0%
14	225	225	225	45	675	13%
15	225	225	225	45	675	0%
16	225	225	225	45	675	0%
17	225	225	225	45	675	0%
18	150	150	150	30	450	-33%
19	150	150	150	30	450	0%
20	100	100	100	20	300	-33%
21	100	100	100	20	300	0%
22	50	50	50	10	150	-50%
23	25	25	25	5	75	-50%
24	0	0	0	0	0	-100%
25	0	0	0	0	0	0%
Switch over*	_	-	-	-	_	-

^{*}Day one or 26 if switching over, not both.

Inactive

Day	Morning mg/kg	Noon mg/kg	Evening mg/kg	Total mg/kg per day	% Change
1*	0	0	0	0	0%
2	0	0	0	0	0%
3	0	0	0	0	0%
4	0	0	0	0	0%
5	0	0	0	0	0%
6	0	0	0	0	0%
7	0	0	0	0	0%
8	0	0	0	0	0%
9	0	0	0	0	0%
10	0	0	0	0	0%
11	0	0	0	0	0%
12	0	0	0	0	0%
13	0	0	0	0	0%
14	0	0	0	0	0%
15	0	0	0	0	0%
16	0	0	0	0	0%
17	0	0	0	0	0%
18	0	0	0	0	0%
19	0	0	0	0	0%
20	0	0	0	0	0%
21	0	0	0	0	0%
22	0	0	0	0	0%
23	0	0	0	0	0%
24	0	0	0	0	0%
25	0	0	0	0	0%
Switch over*	0	0	0	0	0%

^{*}Day one or 26 if switching over, not both.

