3.4. Outcomes

1. Primary Outcome: The mean pain and irritability score on the NCCPC-R through days 11-19 on active drug compared to placebo.

[figure not shown]
An 11-point decrement in the NCCPC-R score with no rebound x 3 days is considered clinically meaningful minimum change (improvement).

Secondary Outcomes:

- 2. For patients who benefited from gabapentin, identification of the lowest dose that was effective in reducing pain scores, as shown by a improvement the NCCPC-R score compared to baseline during day 11-19 on active drug.
- 3. For patients who benefited from gabapentin, identification of the maximal effect dosage as measured by the largest improvement in the NCPCC-R score compared to baseline during days 11-19 on active drug.
- 4. Identification of the latency time in days to the onset of maximum relief of pain and irritability as measured by the NCCPC-R score over days 0-19.
- 5. Adverse Events Collection demonstrates the AE on treatment arm do not exceed the frequency found in the Product Monograph for children receiving gabapentin.
- 6. Exploratory Outcome: PROMIS-57 scores reported by parent/caregiver are improved on the treatment arm compared to the placebo arm.

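### At 15 kg or over, the day 11-19 dose searches include two taper days, and the lowest effective dose is lowest only among doses given in that window

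*Protocol*

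**What the plan says.** The first secondary objective (section 2.2) is to "Identify the optimal dosing of gabapentin in reducing pain and irritability". Two secondary outcomes in section 3.4 serve it.

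- **Lowest effective dose.** Section 3.4 calls for "identification of the lowest dose that was effective in reducing pain scores", judged on the "NCCPC-R score compared to baseline during day 11-19 on active drug". Section 3.10 makes this a rule: "the lowest dose that gives at least an 11 point reduction with no rebound over 3 days in the NCCPC-R score", again from baseline and in days 11-19. The Trial Summary uses a 50% reduction instead; that is a separate matter, and the window is the same.
- **Maximal effect dose.** Sections 3.4 and 3.10 take the dose with the largest improvement from baseline in the same window. There is no three-day condition.

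Three other provisions bear on the point:

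- Section 3.3 holds a child who benefits below the top dose at that dose until the scheduled wean.
- Table 4 schedules the NCCPC-R on days 1, 5, 8, 11 to 19 and 22.
- Under missing data, section 3.10 computes the dose outcomes from observed values only.

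**The concern.** A dose search needs each score to belong to the dose that produced it. On a rising or held dose that is a fair working assumption. On the first days of a taper it is not, because relief gained at the higher dose may last into the lower one. Section 3.10 does not separate rising, held and falling doses.

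The window also sets a floor. A search that starts on day 11 cannot return a step that a child passed through before then. A figure reported simply as the lowest effective dose would hide that limit. Section 2.1 expects the results to help design a larger trial, including its dosing, so readers may take the label at face value.

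**Working it through.** **Inputs.** The two active dosing tables in section 3.3, the NCCPC-R days in Table 4, and the rules in 3.10. The protocol gives no calculated figure for these outcomes, so the check crosses the schedule with the window.

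**Scheduled dose on days 11-19.** Under 15 kg the day 11 row reads "11 13.3 13.3 13.3 40 33", that is, three doses of 13.3 and a total of 40 mg/kg.

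| Days | Under 15 kg (mg/kg/day) | Days | 15 kg or over (mg/day; label in mg/kg/day) |
|---|---|---|---|
| 11-13 | 40 | 11-13 | 600; 40 |
| 14-16 | 50 | 14-17 | 675; 45 |
| 17-19 | 60 | 18-19 | 450; 30 (day 18 marked -33%) |

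**Share of taper days.** Under 15 kg the taper starts on day 20, so 0 of 9. At 15 kg or over, 2/9 = 22%.

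**Maximal effect dose.** With no three-day condition, one best score on day 18 or 19 is enough to assign the child to 450 mg/day.

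**Lowest effective dose.** Count three days as three consecutive scored days, including the first day of the fall. On the schedule, runs at a single dose are:

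- under 15 kg: days 11-13, 14-16 and 17-19;
- 15 kg or over: days 11-13 at 600 mg, and days 14-16 or 15-17 at 675 mg;
- at 450 mg: none, since only days 18 and 19 are scored in the window and days 20-21 are not scored.

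Take a child of 15 kg or over whose score first falls by 11 points on day 16 and stays down to day 19.

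- *All three days at one dose:* there are two days at 675 mg (16, 17) and two at 450 mg (18, 19). No dose qualifies.
- *Days may span doses:* days 16-18 and 17-19 both qualify, and the lowest dose within them is 450 mg.

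The second reading returns a dose the child had already taken on days 8-10 before being escalated. The text allows either reading.

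**Floor on the way up.** Days 1-10 carry the steps labelled 5, 10, 15, 20 and 30 mg/kg/day; the window starts at 40. A child who was not held earlier cannot be assigned any of those five steps from the rising phase.

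**Labels.** At 15 kg or over, the mg/kg column equals mg/15 throughout: 450/15 = 30, 600/15 = 40, 675/15 = 45. It is exact only at 15 kg. At assumed weights of 20, 30 and 45 kg, 600 mg is 30, 20 and 13.3 mg/kg/day.

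**After excluding the taper.** At 15 kg or over the window is days 11-17: 9 - 2 = 7 scored days, three at 600 mg and four at 675 mg.

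**The case against.** **Early responders are covered by the hold rule.** This largely stands. A reader might infer that the outcome is biased upward for every child who improved early. The documents do not support that: a child held at a lower step enters the window at that dose, is scored daily there, and the search can return it. What remains is the child who was not held.

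**The search should then be widened to days 5 and 8.** This is tempting but unsound. Each is a single score on the first day of a new step, so neither can meet the three-day criterion, and crediting it to that day's dose risks the same misattribution as on the taper. The 15 mg/kg/day step is never scored. On the rising schedule the window already contains every step at which the criterion can be tested.

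**The three-day rule blocks the taper dose.** It does so only if all three days must be at one dose, which is not stated. It gives no protection to the maximal effect dose.

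**Carry-over is unlikely.** Section 2.1 gives a half-life of 5 to 7 hours. A day after the step down, between 0.5^(24/5) = 4% and 0.5^(24/7) = 9% of the excess drug remains. That limits persistence of the drug by day 19. It does not show that relief ends as quickly, and it says less about day 18. The documents neither show nor exclude persisting relief.

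**This is detail for an analysis plan.** It might have been, but 3.10 itself fixes the window and the rule, and as fixed they admit the taper days.

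**Conclusion.** The point holds in a limited form. At 15 kg or over, 2 of 9 window days are taper days that nothing excludes. The maximal effect dose is exposed to them directly. The lowest effective dose is exposed only if the three no-rebound days may span doses. A reader might infer that the result is certainly biased downward; the documents do not establish that, because it depends on this unstated reading and on relief outlasting the step down. Under 15 kg there is no taper problem.

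Separately, in both weight groups, for children not held earlier, the outcome is the lowest dose among those given in the window.

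This assumes that the schedule is followed and that three days means three scored days including the first. If three further days are needed after the first, four days at one dose are required, and on the schedule only 675 mg on days 14-17 provides them. How many children will weigh 15 kg or more is not stated. Both outcomes are descriptive, and no primary result depends on how scores are assigned to a dose.

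**What to change.** Amend section 3.10 (and match 3.4) as follows:

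1. Exclude taper days from both dose searches: days 18-19 at 15 kg or over.
2. For the lowest effective dose, require the three no-rebound days to be scored days at the same rising or held dose, and say whether the first day counts.
3. Use the dose the child actually took, in mg and per actual weight, rather than the table label.
4. Report the outcome as *lowest effective dose among doses given on days 11 to the start of the taper*.
5. Show scores on days 5 and 8 descriptively, but do not use them to assign a lowest effective dose.

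No dose, schedule or assessment changes, and no new data are needed. The cost is two fewer scored days at 15 kg or over for these outcomes (7 instead of 9). A child who first responds on day 16 or 17 would then have no confirmed lowest dose, and should be reported as such.
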